**Time (time is in reference to Study Drug administration):**

- 1 Pre-dose

## **Appendix B     List of Laboratory Analytes**

## Appendix B List of Laboratory Analytes

Based on emerging data from this or future studies, additional tests not listed below may be performed on stored samples to better characterize the profile of AKCEA-ANGPTL3-LRX or other similar oligonucleotides.

Clinical Chemistry	Screening Tests	Hematology	Inflammatory
Panel			

 
Sodium
 
Potassium
 
Chloride
 
Bicarbonate
 
Total protein
 
Albumin
 
Calcium
 
Magnesium
 
Phosphorus
 
Glucose
 
Insulin
 
BUN
 
Creatinine
 
Uric Acid
 
Total bilirubin
 
Direct (conjugated) bilirubin
 
Indirect (unconjugated) bilirubin
 
ALT
 
AST
 
Alkaline phosphatase
 
Creatinine kinase
 
Cys-C
 
	
 
Hepatitis B surface antigen
 
Hepatitis C antibody
 
HIV antibody
 
FSH (women only)
 
Serum <math>\beta</math>hCG
 
	
 
Blood viscosity
 
Red blood cells
 
Hemoglobin
 
Hematocrit
 
MCV, MCH, MCHC
 
Platelets count
 
Platelets function
 
White blood cells
 
WBC Differential (% and absolute) 
 
Neutrophils
 
Eosinophils
 
Basophils
 
Lymphocytes
 
Monocytes
 
 
 
	
 
Hs-CRP
 
Cytokine panel 
 
IL-1b,
 
IL-6,
 
IL-8
 
 
 

Fasting Lipid Panel			

 
Total cholesterol
 
Total ApoB
 
ApoB-100
 
ApoB-48
 
LDL cholesterol
 
HDL cholesterol
 
Total Triglycerides
 
CM triglycerides
 
VLDL cholesterol
 
VLDL triglycerides
 
Non-HDL cholesterol
 
	
 
ANGPTL3
 
ANGPTL4
 
ANGPTL8
 
ApoA-I
 
ApoB
 
ApoC-III
 
		
	Specialized Lipoprotein and post-prandial Analyses 	Thyroid Panel	Urinalysis
	
 
Lipoprotein particle analysis
 
Oxidized chylomicrons and VLDLs
 
Isoprostanes
 
HDL function and characterization
 
Lipoprotein subclass analysis
 
Newly formed CM and LDL, IDL, HDL kinetics
 
Post-prandial lipid panel
 
Post-prandial platelet count and function
 
Post-prandial glucose
 
	
 
TSH
 
Free T4
 
	
 
Color
 
Appearance
 
Specific gravity
 
pH
 
Protein
 
Blood
 
Ketones
 
Urobilinogen
 
Glucose
 
Bilirubin
 
Leukocyte esterase
 
Nitrate
 
Microscopic examination
 
P/C Ratio (UPCR)
 
A/C Ratio (UACR)
 

		Pharmacokinetics and Immunogenicity	24 Hour Urine Test
		
 
AKCEA-ANGPTL3-LRX levels in plasma
 
Anti- AKCEA-ANGPTL3-LRX antibodies in plasma
 
	
 
Creatinine clearance
 
Protein
 
Albumin
 

		Genetic Testing	
		
 
Molecular confirmation of FCS
 
Genetic sequencing of FCS causing genes
 
	

1 Scope of specialized lipoprotein analyses will be determined based on results from fasting lipid panel

- 2 Plasma PK samples may also be used for profiling of drug binding proteins, bioanalytical method validation, stability assessments, metabolite assessments, testing of additional exploratory pharmacodynamics markers, immunogenicity testing (or possibly for immunogenicity assay development and/or validation), or to assess other actions of AKCEA-ANGPTL3-LRX with plasma constituents

**Appendix B List of Laboratory Analytes *Continued***

- 3 If the genotype is not already available, blood will be collected to assess genetic evidence of null loss-of-function for LPL. May not be collected if adequate genetic data are available in medical history or if patient does not consent to genetic testing
- 4 Will be performed on abnormal findings unless otherwise specified

## **Appendix C PK Sampling Schedule**

**Appendix C PK Sampling Schedule**

D1	D29	D43	D57	D71	D92	D120	D148	D176
Pre-dose	Pre-dose	Pre-dose	Pre-dose	Pre-dose	Anytime	Anytime	Anytime	Anytime

Note: D = Day

**Appendix D     Grading Scale for Adverse Events Relating to  
Laboratory Abnormalities**

## Appendix D Grading Scale for Adverse Events Relating to Laboratory Abnormalities

The following grading recommendations for adverse events relating to lab test abnormalities are based upon the Common Terminology Criteria for Adverse Events (CTCAE) Version 4.03, June 2010.

Adverse Event	Mild	Moderate	Severe
Hematology			
aPTT prolonged	>ULN - 1.5 x ULN	>1.5 - 2.5 x ULN	>2.5 x ULN; hemorrhage
Eosinophils increased r	650 - 1,500 cell/mm 	1,501 - 5,000 cell/mm 	>5,000 cell/mm 
Fibrinogen decreased	<1.0 - 0.75 x LLN or <25% decrease from baseline	<0.75 - 0.5 x LLN or 25 - <50% decrease from baseline	<0.5 x LLN or ≥50% decrease from baseline
Hemoglobin decreased (Anemia)	Hemoglobin (Hgb) <LLN - 10.0 g/dL; <LLN - 6.2 mmol/L; <LLN - 100 g/L	Hgb <10.0 - 8.0 g/dL; <6.2 - 4.9 mmol/L; <100 - 80g/L	Hgb <8.0 g/dL; <4.9 mmol/L; <80 g/L; transfusion indicated
Hemoglobin increased	Increase in >0 - 2 g/dL above ULN or above baseline if baseline is above ULN	Increase in >2 - 4 g/dL above ULN or above baseline if baseline is above ULN	Increase in >4 g/dL above ULN or above baseline if baseline is above ULN
INR increased	>1 - 1.5 x ULN; >1 - 1.5 times above baseline if on anticoagulation	>1.5 - 2.5 x ULN; >1.5 - 2.5 times above baseline if on anticoagulation	>2.5 x ULN; >2.5 times above baseline if on anticoagulation
Lymphocyte count decreased	<LLN - 800/mm  ; <LLN - 0.8 x 10  /L	<800 - 500/mm  ; <0.8 - 0.5 x 10  /L	<500 /mm  ; <0.5 x 10  /L
Lymphocyte count increased	-	>4000/mm  - 20,000/mm 	>20,000/mm 
Neutrophil count decreased	<LLN - 1500/mm  ; <LLN - 1.5 x 10  /L	<1500 - 1000/mm  ; <1.5 - 1.0 x 10  /L	<1000/mm  ; <1.0 x 10  /L
Platelet count decreased	<LLN - 75,000/mm  ; <LLN - 75.0 x 10  /L	<75,000 - 50,000/mm  ; <75.0 - 50.0 x 10  /L	<50,000/mm  ; <50.0 x 10  /L
White blood cell decreased	<LLN - 3000/mm  ; <LLN - 3.0 x 10  /L	<3000 - 2000/mm  ; <3.0 - 2.0 x 10  /L	<2000/mm  ; <2.0 x 10  /L
Chemistry			
Acidosis	pH <normal, but ≥7.3	-	pH <7.3
Alanine aminotransferase increased	>ULN - 3.0 x ULN	>3.0 - 5.0 x ULN	>5.0 x ULN
Alkaline phosphatase increased	>ULN - 2.5 x ULN	>2.5 - 5.0 x ULN	>5.0 x ULN
Alkalosis	pH >normal, but ≤7.5	-	pH >7.5
Aspartate aminotransferase increased	>ULN - 3.0 x ULN	>3.0 - 5.0 x ULN	>5.0 x ULN
Blood bilirubin increased	>ULN - 1.5 x ULN	>1.5 - 3.0 x ULN	>3.0 x ULN
Cardiac troponin I increased	Levels above the upper limit of normal and below the level of myocardial infarction as defined by the manufacturer	-	Levels consistent with myocardial infarction as defined by the manufacturer

Appendix D Grading Scale for Adverse Events Relating to Laboratory Abnormalities *Continued*

Adverse Event	Mild	Moderate	Severe
Cardiac troponin T increased	Levels above the upper limit of normal and below the level of myocardial infarction as defined by the manufacturer	-	Levels consistent with myocardial infarction as defined by the manufacturer
CD4 lymphocytes decreased	<LLN - 500/mm  ; <LLN - 0.5 x 10  /L	<500 - 200/mm  ; <0.5 - 0.2 x 10  /L	<200/mm  ; <0.2 x 10  /L
CPK increased*	>ULN - <6 x ULN	6 - 10 x ULN	>10 x ULN
Creatinine increased	>1 - 1.5 x baseline; >ULN - 1.5 x ULN	>1.5 - 3.0 x baseline; >1.5 - 3.0 x ULN	>3.0 x baseline; >3.0 x ULN
GGT increased	>ULN - 2.5 x ULN	>2.5 - 5.0 x ULN	>5.0 x ULN
Hypercalcemia	Corrected serum calcium of >ULN - 11.5 mg/dL; >ULN - 2.9 mmol/L; ionized calcium >ULN - 1.5 mmol/L	Corrected serum calcium of >11.5 - 12.5 mg/dL; >2.9 - 3.1 mmol/L; ionized calcium >1.5 - 1.6 mmol/L; symptomatic	Corrected serum calcium of >12.5 mg/dL; >3.1 mmol/L; ionized calcium >1.6 mmol/L; hospitalization indicated
Hyperglycemia	Fasting glucose value >ULN - 160 mg/dL; Fasting glucose value >ULN - 8.9 mmol/L	Fasting glucose value >160 - 250 mg/dL; Fasting glucose value >8.9 - 13.9 mmol/L	>250 mg/dL; >13.9 mmol/L; hospitalization indicated
Hyperkalemia	>ULN - 5.5 mmol/L	>5.5 - 6.0 mmol/L	>6.0; hospitalization indicated
Hypermagnesemia	>ULN - 3.0 mg/dL; >ULN - 1.23 mmol/L	-	>3.0 mg/dL; >1.23 mmol/L
Hypernatremia	>ULN - 150 mmol/L	>150 - 155 mmol/L	>155 mmol/L; hospitalization indicated
Hyperuricemia	>ULN - 10 mg/dL (0.59 mmol/L) without physiologic consequences	-	>ULN - 10 mg/dL (0.59 mmol/L) with physiologic consequences
Hypocalbuminemia	<LLN - 3 g/dL; <LLN - 30 g/L	<3 - 2 g/dL; <30 - 20 g/L	<2 g/dL; <20 g/L
Hypocalcemia	Corrected serum calcium of <LLN - 8.0 mg/dL; <LLN - 2.0 mmol/L; ionized calcium <LLN - 1.0 mmol/L	Corrected serum calcium of <8.0 - 7.0 mg/dL; <2.0 - 1.75 mmol/L; ionized calcium <1.0 - 0.9 mmol/L; symptomatic	Corrected serum calcium of <7.0 mg/dL; <1.75 mmol/L; ionized calcium <0.9 mmol/L; hospitalization indicated
Hypoglycemia	<LLN - 55 mg/dL; <LLN - 3.0 mmol/L	<55 mg/dL; <3.0 mmol/L	<40 mg/dL (<2.2 mmol/L) AND requires assistance of another person to actively administer carbohydrates, glucagon, or take other corrective actions f
Hypokalemia	<LLN - 3.0 mmol/L	<LLN - 3.0 mmol/L; symptomatic; intervention indicated	<3.0 mmol/L; hospitalization indicated
Hypomagnesemia	<LLN - 1.2 mg/dL; <LLN - 0.5 mmol/L	<1.2 - 0.9 mg/dL; <0.5 - 0.4 mmol/L	<0.9 mg/dL; <0.4 mmol/L
Hyponatremia	<LLN - 130 mmol/L	-	<130 mmol/L
Hypophosphatemia	<LLN - 2.5 mg/dL; <LLN - 0.8 mmol/L	<2.5 - 2.0 mg/dL; <0.8 - 0.6 mmol/L	<2.0 mg/dL; <0.6 mmol/L
Lipase increased	>ULN - 1.5 x ULN	>1.5 - 2.0 x ULN	>2.0 x ULN
Serum amylase increased	>ULN - 1.5 x ULN	>1.5 - 2.0 x ULN	>2.0 x ULN

**Appendix D    Grading Scale for Adverse Events Relating to Laboratory Abnormalities**  
***Continued***

Adverse Event	Mild	Moderate	Severe
Urine			
Proteinuria			
Adults	1+ proteinuria; urinary protein <1.0 g/24 hrs	2+ proteinuria; urinary protein 1.0 - 3.4 g/24 hrs; Urine P/C (Protein/Creatinine) ratio 0.5 - 1.9	Urinary protein ≥3.5 g/24 hrs; Urine P/C >1.9
Children	-		
Hematuria	Asymptomatic; clinical or diagnostic observations only; intervention not indicated	Symptomatic; urinary catheter or bladder irrigation indicated	Gross hematuria; transfusion, IV medications or hospitalization indicated; elective endoscopic, radiologic or operative intervention indicated

†Grading for this parameter is derived from the Toxicity Grading Scale for Healthy Adult and Adolescent Volunteers Enrolled in Preventive Vaccine Clinical Trials. Sept 2007

\*Grading for this parameter is derived from the Division of AIDS (DAIDS) Table for Grading the Severity of Adult and Pediatric Adverse Events Version 2.0, Nov 2014

‡Modified for consistency with the ADA and Endocrine Society Guidelines (Sequist ER, Anderson J, Childs B, et al. Hypoglycemia and Diabetes: A Report of a Workgroup of the American Diabetes Association and The Endocrine Society. Diabetes Care 2013;36:1384-95)

## **Appendix E     Post-prandial Meal, Sampling Schedule, and Assessment**

## Appendix E Post-prandial Meal, Sampling Schedule, and Assessment

Post-prandial assessment for lipoproteins metabolism (lipoprotein kinetics: newly formed CM, VLDL, IDL, LDL and HDL) will be performed as follows. A radiolabelled meal supplemented with a labeled tracer,  $^3\text{H}$ -palmitate (300 $\mu\text{Ci}$ , [REDACTED] Canada), will be sonicated into the liquid meal. Palmitate is a fatty acid that is a common constituent of any diet. The  $^3\text{H}$ -palmitate tracer emits weak radioactivity, equivalent to an X-ray. Since dietary palmitate is incorporated into chylomicrons as they are formed in the enterocytes of the gut, this enables monitoring the appearance and clearance of newly-formed chylomicrons from circulation. The methodology to be applied for studying post-prandial kinetics of chylomicrons appearance and clearance is well-established (Mittendorfer et al. 2003; Bickerton et al. 2007; Normand-Lauziere et al. 2010).

A liquid meal (similar to a milkshake) containing a small amount (300 $\mu\text{Ci}$ ) of radiolabelled fatty acids ( $^3\text{H}$ -palmitate) will be provided. The liquid meal will provide about a third of the daily caloric requirements. From 1 hr prior to 9 hrs after the ingestion of the meal, two stable isotope tracers will be continuously infused. A primed (1.6  $\text{mmol}/\text{kg}$ ) continuous (0.05  $\text{mmol}/\text{kg}/\text{min}$ ) infusion of [1,1,2,3,3- $^2\text{H}$ ]-glycerol [REDACTED] will be administered as previously described (Normand-Lauziere et al. 2010). To document VLDL, IDL, LDL and HDL kinetics, L-[5,5,5-D3] leucine (10  $\text{mmol}/\text{kg}$ ) will be injected as a bolus intravenously and then by continuous infusion (10  $\text{mmol}\cdot\text{kg}$  body weight·h) (Tremblay et al. 2006). Glycerol appearance rates will be calculated using Steele's non-steady state equation assuming a volume of distribution of 230ml/kg (Gastaldelli et al. 1999). The isotopic enrichment of leucine in the apolipoproteins will be expressed as tracer/tracee ratio (%) using standardized formulas (Cobelli et al. 1987).

Blood samples will be drawn at intervals before and after the ingestion of the radiolabelled meal on days prior to and after the Treatment phase as noted in the table below. A standardized meal will be given to the participants after the 9 hr blood draw. Blood will be collected in tubes containing Na2EDTA and Orlistat (30 mg/ml, [REDACTED] Canada) to prevent *in vitro* triacylglycerol lipolysis and separate samples will be collected in NaF tubes for plasma glucose determination.

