## **Appendix E     Post-prandial Meal, Sampling Schedule, and Assessment**

## Appendix E Post-prandial Meal, Sampling Schedule, and Assessment

Post-prandial assessment for lipoproteins metabolism will be performed using a radiolabelled meal supplemented with a labeled tracer,  $^3\text{H}$ -palmitate ( $300\mu\text{Ci}$ , [REDACTED] Canada), sonicated into the liquid meal. Palmitate is a fatty acid that is a common constituent of any diet. The  $^3\text{H}$ -palmitate tracer emits weak radioactivity, equivalent to an X-ray. Since dietary palmitate is incorporated into chylomicrons as they are formed in the enterocytes of the gut, this enables monitoring the appearance and clearance of newly-formed chylomicrons from circulation. The methodology to be applied for studying post-prandial kinetics of chylomicrons appearance and clearance is well-established (Mittendorfer et al. 2003; Bickerton et al. 2007; Normand-Lauziere et al. 2010).

A liquid meal (similar to a milkshake) containing a small amount ( $300\mu\text{Ci}$ ) of radiolabelled fatty acids ( $^3\text{H}$ -palmitate) will be provided. The liquid meal will provide about a third of the daily caloric requirements. From 1 hr prior to 9 hrs after the ingestion of the meal, a constant infusion of  $[\text{U}-^{13}\text{C}]\text{-K}$  palmitate ( $0.01\mu\text{mol}/\text{kg}/\text{min}$  in 100 ml 25% human serum albumin; [REDACTED] and a primed ( $1.6\mu\text{mol}/\text{kg}$ ) continuous ( $0.05\mu\text{mol}/\text{kg}/\text{min}$ ) infusion of  $[1,1,2,3,3-^2\text{H}]\text{-glycerol}$  [REDACTED] will be administered as previously described (Normand-Lauziere et al. 2010). Plasma palmitate and glycerol appearance rates will be calculated using Steele's non-steady state equation assuming a volume of distribution of 90ml/kg and 230ml/kg, respectively (Gastaldelli et al. 1999).

Blood samples will be drawn at intervals before and after the ingestion of the radiolabelled meal on days prior to and after the Treatment phase as noted in the table below. A standardized meal will be given to the participants after the 9 hr blood draw. Blood will be collected in tubes containing  $\text{Na}_2\text{EDTA}$  and Orlistat ( $30\mu\text{g}/\text{ml}$ , [REDACTED] Canada) to prevent *in vitro* triacylglycerol lipolysis and separate samples will be collected in  $\text{NaF}$  tubes for plasma glucose determination.

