## PROTOCOL AMENDMENT

**Protocol Number:** ISIS 703802-CS3

**Protocol Title:** **A Phase 2 Open-Label Study to Assess the Pharmacodynamics, Pharmacokinetics, Safety and Tolerability of AKCEA-ANGPTL3-LRX (ISIS 703802) Administered Subcutaneously to Patients with Familial Chylomicronemia Syndrome (FCS)**

**Amendment Number:** Protocol Amendment 1

**Amendment Date:** 26 OCTOBER 2017

---

The purpose of this protocol amendment is to implement the following modifications to Protocol ISIS 703802-CS3 Original Protocol dated 20 July 2017:

- Change in language for Exclusion Criteria on how to confirm urine laboratory tests
- Further clarify in the Synopsis that subjects who are on a stable diet do not need to have a six week diet stabilization period during screening period
- Include language requested by Health Authority
- Include a measure of abdominal pain assessment (this change is not included in the table below, it has resulted in one additional line in the Schedule of Procedures, Appendix A).
- Appendix E was modified to remove the stable isotope tracer [U-C]-K palmitate and replace it by L-[5,5,5-D3] leucine, allowing to document kinetics of all apolipoprotein B containing lipoproteins. [Section 6.1.2](#) has also been updated to align with these changes.
- An objective has been added in order to align with the update to the post-prandial assessment: To evaluate postprandial lipoprotein kinetics: of CM, VLDL, IDL, LDL and HDL
- Clarify various inconsistencies:
  - Screening period duration
  - Fibrates have been deleted from disallowed concomitant therapy
  - Change to contact for SAE reporting
  - Plasma TG is being updated to serum TG for efficacy analysis
  - Urine samples will not be archived
  - Appendix A has updates, including deletion of FSH at week 1, deletion of FPG since this parameter is being measured with the chemistry panel, platelet aggregation has been deleted from screening visit, footnote (a, g, l and m) in SOP have changed.

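### Amendment 1, Appendix E, prints the glycerol tracer dose in mmol where the original protocol gives the same figures in µmol; check the source page before any infusion

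*Combined protocol and SAP*

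**What the plan says.** Appendix E of the original protocol gives labelled glycerol as a prime of 1.6 µmol/kg followed by a "continuous ( $0.05\mu\text{mol}/\text{kg}/\text{min}$ ) infusion of" the tracer. Amendment 1, Appendix E, keeps the numbers, the compound and the cited method, but the prime reads 1.6 mmol/kg and the rate reads "continuous (0.05 $\text{mmol}/\text{kg}/\text{min}$ ) infusion of". It describes the infusates as tracers and gives the timing: "From 1 hr prior to 9 hrs after the ingestion of the meal, two stable isotope tracers will be continuously infused". The glycerol appearance rate is then calculated "assuming a volume of distribution of 230ml/kg", the same volume as in the original protocol.

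The amendment's list of purposes explains the revision of this appendix as follows: "Appendix E was modified to remove the stable isotope tracer", with labelled leucine taking the place of labelled palmitate. It mentions no change to glycerol. The change table prints glycerol in mmol in both its WAS and its IS text.

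Two other quantities in the amended appendix have similar units. The new tracer is given as "leucine (10 $\text{mmol}/\text{kg}$ ) will be injected as a bolus intravenously and then by continuous infusion", the infusion being 10 mmol/kg/h. The blood-tube additive reads "Orlistat (30 mg/ml", where the original protocol has 30 µg/ml.

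**The concern.** The amended text states an intravenous dose. If it means what it prints, each of two sessions per patient delivers a gram-scale glycerol load in place of a tracer. That would be unsafe. It would also add substantially to the pool whose appearance rate is being estimated, whereas a tracer method needs the added amount to be negligible. The procedure supplies the secondary objective on post-prandial TG and lipoprotein kinetics (Section 1.2). Because the change table shows mmol on both sides, someone comparing old and new text there would see no change of unit.

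**Working it through.** No figure derived in the plan depends on this dose, so there is nothing of the plan's own to reproduce. The check is direct arithmetic on the printed doses.

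Inputs from the documents:
- Glycerol prime 1.6 and rate 0.05 per minute, per kg: mmol in Amendment 1, µmol in the original protocol.
- Duration: 10 h (1 h before to 9 h after the meal) in Amendment 1, Appendix E; 9 h in Amendment 1, Section 6.1.2.
- Glycerol volume of distribution: 230 ml/kg.
- Leucine: 10 mmol/kg bolus, then 10 mmol/kg/h (Amendment 1 only).

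Assumptions not in the documents: molar masses of 97.12 g/mol (five-deuterium glycerol) and 134.19 g/mol (three-deuterium leucine); body weight 70 kg, range 50 to 100 kg.

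**Glycerol per kg** = prime + rate × minutes.
- 10 h: 1.6 + 0.05 × 600 = 31.6 mmol/kg as printed, against 31.6 µmol/kg in the original unit.
- 9 h: 1.6 + 0.05 × 540 = 28.6 mmol/kg.

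**Glycerol in grams** = total per kg × weight × molar mass.
- 10 h, 70 kg: 0.0316 mol/kg × 70 kg × 97.12 g/mol ≈ 215 g (153 to 307 g over 50 to 100 kg).
- 9 h, 70 kg: about 194 g (139 to 278 g).
- In µmol, 10 h, 70 kg: about 0.21 g.

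**Effect on the pool, with the protocol's own volume and no weight assumption.**
- Prime: 1.6 / 0.230 = 6.96 mmol/L as printed, against 6.96 µmol/L.
- Infusion before clearance: 0.05 / 0.230 = 0.217 mmol/L per minute, against 0.217 µmol/L per minute.

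**Prime-to-rate ratio**: 1.6 / 0.05 = 32 min in both versions. The regimens are identical apart from the prefix.

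**Leucine as printed**: 10 + 10 × 10 = 110 mmol/kg over 10 h. Then 0.110 × 70 × 134.19 ≈ 1,033 g, about 1 kg at 70 kg (738 to 1,476 g over 50 to 100 kg). Over 9 h it is 100 mmol/kg, about 939 g at 70 kg.

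**Could the prefix have been lost in reading the PDF?** In the same paragraph of Amendment 1, Appendix E, the radiolabel keeps its micro sign: "containing a small amount (300 $\mu\text{Ci}$ ) of radiolabelled fatty acids". In the change table, one WAS sentence carries the palmitate rate with a micro prefix and then glycerol with milli. Across the change table and Appendix E, all ten glycerol and leucine units read mmol (four glycerol and two leucine in the table, two and two in the appendix).

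**The case against.** The strongest reply is that the whole point turns on a page that cannot be seen here, and a reading fault is not an error in the plan. The amended file does have damaged symbols elsewhere. The lambda is gone from the half-life row of the glossary, a delta stands in the name of the 2'-MOE chemistry in Section 2.5.2, and a dagger reads as a letter in Appendix D. The WAS text of the change table is itself noisy: it gives palmitate as 0.04 where the original protocol has 0.01, and its isotope label is incomplete. It also prints mmol where it claims to reproduce text that reads µmol. That points to a lost symbol, whether in reading or in the sponsor's typesetting, more than to a decision to change the dose.

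Much of this stands, and it is why the point is conditional. What does not stand is the step from a lost symbol to a pure reading fault. The micro sign survives in the activity of the meal and in the palmitate rate beside the glycerol figures, so a loss when the amendment was prepared is the likelier explanation.

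It is also fair that a site familiar with the cited method would probably notice. A written intravenous dose should not rely on that.

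A reader might infer that the sponsor raised the dose 1000-fold, or that patients received gram quantities. The documents support neither. No dose change is declared, the text still calls the infusates tracers, and nothing reports what was infused.

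**Conclusion.** The concern holds in conditional form. As the text reads, the glycerol dose in Amendment 1, Appendix E, is exactly 1000 times the original protocol's and inconsistent with its own description as a tracer: 31.6 mmol/kg over 10 h or 28.6 over 9 h. Those per-kg figures and the concentration figures need no outside input. The gram figures rest on the assumed molar masses and weights, but no plausible weight turns them into tracer amounts. It is a must-fix only if the source page prints milli.

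Three limits apply. First, leucine at about 1 kg per session is implausible as a tracer, and a reader might infer that the unit must be µmol. The documents contain no earlier leucine dose, and the cited method is not available here, so the correct value cannot be derived from them. Second, Orlistat is a tube reagent and not a patient dose. Third, a reader might infer that the trial's main results are compromised. The primary fasting TG endpoint does not use the tracer data and is not affected. The glycerol appearance rate is not named among the secondary objectives (Section 1.2) or the efficacy endpoints (Section 10.1.1). The consequence is for infusion safety and for the secondary post-prandial kinetics.

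**What to change.** Check the source page of Amendment 1, Appendix E, and the matching rows of the change table. If they print micro, no change is needed. If they print milli:
- restore glycerol to a 1.6 µmol/kg prime and 0.05 µmol/kg/min in Appendix E and in the change table;
- restore Orlistat to 30 µg/ml;
- verify the leucine bolus and infusion units against the cited method and correct them as that source requires;
- notify the site before any infusion under Amendment 1.

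The cost is one page check and, if milli is confirmed, a text correction and a site notice. No patients, samples or procedures are added.
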